6.1.1.2 Secondary Endpoints

There are multiple secondary endpoints in this study, described in the following subsections.

For the secondary endpoints which consider duration of time on the study, duration of time on the study will be calculated as:

$$\text{Date of Last Visit} - \text{Date of Baseline Visit} + 1$$

6.1.1.2.1 PCS – Pain Catastrophising Scale

The Pain Catastrophising Scale (PCS) is a 13 item questionnaire around thoughts and emotions experienced during pain, with each question on a 5 point scale (0 = 'Not at all' to 4 = 'All the time'). There are three subscales of PCS: Rumination (thinking deeply), exaggeration and helplessness. [Table 2](#) shows an overview of the items which belong to each domain.

Table 2 Overview of Domains for PCS ([5](#))

Domain	Items
Rumination	8, 9, 10, 11
Exaggeration	6, 7, 13
Helplessness	1, 2, 3, 4, 5, 12

Total scores and domain scores are derived by summing the scores of the individual items. The highest possible score of PCS is 52, and a total score of ≥ 20 indicates a clinically relevant level of catastrophisation. PCS will be considered both in terms of individual domain scores and total scores. PCS total score will be analysed as a continuous variable as well as a dichotomous variable (<20 vs ≥ 20).

For the handling of missing data when deriving PCS scores, see Section [7.4](#).

PCS is collected at all visits (Inclusion visit, V1, V2, V3, V4, V5, V6 and any additional visits in the case of discontinuation of Tofacitinib).

6.1.1.2.2 CSQ – Coping Strategies Questionnaire

The Coping Strategies Questionnaire (CSQ) evaluates cognitive coping and, in its French version, is split into 5 domains: “Distraction”, “Catastrophising”, “Distancing from Pain”, “Ignoring Pain Sensations” and “Praying”. The CSQ consists of 21 items in total and for each item, subjects rate the frequency of their use of each coping strategy on a 4-point Likert-type scale. CSQ is collected on the CRF as the following: 1: Never, 2: Sometimes, 3: Often and 4: Very often. In order to consider values comparable to the standard CSQ French Version, the following mapping will be done.

CSQ Text Value	CRF Value	Map to standard value
Never	1	0
Sometimes	2	1
Often	3	2
Very Often	4	3

This endpoint is considered in terms of the 5 domains, and a total score is not considered for CSQ. Domain scores are derived by summing the individual items scores that make-up the domain. Details of the 5 domains are provided below.

Domain	Items as numbered on CRF	Domain Score Range
Distraction	2, 10, 11, 19, 20	0 – 15
Catastrophising	3, 9, 15, 18	0 -12
Distancing from Pain	1, 5, 13, 21	0 – 12
Ignoring Pain Sensations	6, 7, 8, 14, 16	0 – 15
Praying	4, 12, 17	0 - 9

CSQ is collected at all visits (Inclusion visit, V1, V2, V3, V4, V5, V6 and any additional visits in the case of discontinuation of Tofacitinib).

For the handling of missing CSQ data, see Section [7.5](#).

6.1.1.2.3 LDA

Low Disease Activity (LDA) is a binary endpoint and can be assessed in four different ways using DAS28-4 ESR, DAS28-4 CRP, SDAI and CDAI. The individual criteria for the four different ways of measuring LDA are:

- DAS28-4 ESR ≤ 3.2
- DAS28-4 CRP ≤ 3.2
- SDAI ≤ 11
- CDAI ≤ 10

Each criteria will be analysed separately.

All of the LDA factor individual components are collected at all visits (Inclusion visit, V1, V2, V3, V4, V5, V6 and any additional visits in the case of discontinuation of Tofacitinib).

6.1.1.2.4 DAS28-4 ESR

The 28-joint Disease Activity Score erythrocyte sedimentation rate (DAS28-4 ESR) is a composite endpoint, calculated using 4 variables (represented by '-4' in the name). The calculation of DAS28-4 ESR is as follows:

$$0.56 * \text{sqrt}(TJC) + 0.28 * \text{sqrt}(SJC) + 0.70 * \ln(\text{ESR}) + 0.014 * \text{PtGA}$$

With ESR in mm/h, \ln = natural logarithm and PtGA is patient global assessment in mm.

DAS28-4 ESR contributes to the assessment of patient LDA and patient remission, and is also summarised in its own right.

The individual components of DAS28-4 ESR are collected at all visits (Inclusion visit, V1, V2, V3, V4, V5, V6 and any additional visits in the case of discontinuation of Tofacitinib).

6.1.1.2.5 DAS28-4 CRP

The 28-joint Disease Activity Score C Reactive Protein with 4 variables (DAS28-4 CRP) is, similarly to DAS28-4 ESR, a composite endpoint calculated using 4 variables.

However, instead of ESR, CRP is used and the calculation varies slightly. The calculation of DAS28-4 CRP is as follows:

$$0.56 * \text{sqrt}(TJC) + 0.28 * \text{sqrt}(SJC) + 0.36 * \ln(\text{CRP}+1) + 0.014 * \text{PtGA} + 0.96$$

With CRP in mg/l, \ln = natural logarithm and PtGA in mm.

DAS28-4 CRP contributes to the assessment of patient LDA and patient remission, and is also summarised in its own right.

The individual components of DAS28-4 CRP are collected at all visits (Inclusion visit, V1, V2, V3, V4, V5, V6 and any additional visits in the case of discontinuation of Tofacitinib).

6.1.1.2.6 SDAI

The Simplified Disease Activity Index (SDAI) is a composite end point, calculated as

$$\text{TJC} + \text{SJC} + \text{PtGA} + \text{PhGA} + \text{CRP}$$

Where TJC is tender joint count (28), SJC is swollen joint count (28), PtGA is patient global assessment in cm and PhGA is physician global assessment in cm, and CRP is C-reactive protein in mg/dL.

The individual components of SDAI are collected at all visits (Inclusion visit, V1, V2, V3, V4, V5, V6 and any additional visits in the case of discontinuation of Tofacitinib).

6.1.1.2.7 CDAI

The Clinical Disease Activity Index (CDAI) is a composite end point, calculated as

$$\text{TJC} + \text{SJC} + \text{PtGA} + \text{PhGA}$$

Where TJC is tender joint count (28), SJC is swollen joint count (28), PtGA is patient global assessment in cm and PhGA is physician global assessment in cm.

The individual components of CDAI are collected at all visits (Inclusion visit, V1, V2, V3, V4, V5, V6 and any additional visits in the case of discontinuation of Tofacitinib).

6.1.1.2.8 Patient Remission

Patient remission will be calculated using 5 separate definitions:

- DAS28-4 ESR < 2.6
- DAS28-4 CRP < 2.6
- SDAI \leq 3.3
- CDAI \leq 2.8
- ACR-EULAR 2011 Boolean criteria should be met

The ACR-EULAR 2011 Boolean criteria is defined in more detail below, in Section 6.1.1.2.9.

6.1.1.2.9 ACR-EULAR 2011 Boolean Criteria

The America College of Rheumatology-European League Against Rheumatism (ACR-EULAR) 2001 Boolean criteria is derived as:

$$\text{ACR_Remission} = 1, \text{ if } \text{SJC} \leq 1, \text{ TJC} \leq 1, \text{ CRP} \leq 1 \text{ mg/dL, and } \text{PtGA} \leq 1 \text{ cm}$$

$$\text{ACR_Remission} = 0, \text{ Otherwise.}$$

Where CRP is measured in mg/dL.

The proportion of patients which meet the ACR-EULAR 2011 Boolean criteria at Visit X is then calculated as:

No. of patients with ACR-EULAR met at Visit X / Total Number of patients with non-missing ACR-Eular at Month X.

The individual factors of ACR-EULAR 2011 Boolean Criteria are collected at all visits (Inclusion visit, V1, V2, V3, V4, V5, V6 and any additional visits in the case of discontinuation of Tofacitinib).

6.1.1.2.10 DAS28 (EULAR Criteria)

The DAS28 EULAR criteria to evaluate patient response to treatment is categorised by good responder patient, moderate responder patient, non-responder patient and non-evaluable patient based on patients DAS28-4 CRP score and the decrease in DAS28-4 CRP compared to Visit 0. [Table 3](#) below gives further detail of the categorisation.

Table 3 Evaluation of patient response to treatment using DAS28 (EULAR Criteria)

DAS28 at visit	Decrease in DAS28 compared to V0		
	>1.2	>0.6 and ≤1.2	≤0.6
≤3.2	Good responder	Moderate responder	Non-responder
>3.2 and ≤5.1	Moderate responder	Moderate responder	Non-responder
>5.1	Moderate responder	Non-responder	Non-responder

The DAS-28 EULAR Criteria will also be derived based on the DAS28-4 ESR score using the same approach as above.

The individual components of DAS28-4 CRP and DAS28-4 ESR, which are the composite endpoints used in this criteria, are collected at all visits (Inclusion visit, V1, V2, V3, V4, V5, V6 and any additional visits in the case of discontinuation of Tofacitinib).

6.1.1.2.11 TJC

Tender Joint Count (TJC) (28) is the count of the total number of tender joints out of a possible 28 joints which are checked at the visit.

TJC is collected at all visits (Inclusion visit, V1, V2, V3, V4, V5, V6 and any additional visits in the case of discontinuation of Tofacitinib).

6.1.1.2.12 SJC

Swollen Joint Count (SJC) (28) is the count of the total number of swollen joints out of a possible 28 joints which are checked at the visit.

SJC 28 is collected at all visits (Inclusion visit, V1, V2, V3, V4, V5, V6 and any additional visits in the case of discontinuation of Tofacitinib).

6.1.1.2.13 Morning Stiffness

The duration of morning stiffness is measured in minutes.

Duration of morning stiffness is collected at all visits (Inclusion visit, V1, V2, V3, V4, V5, V6 and any additional visits in the case of discontinuation of Tofacitinib).

6.1.1.2.14 EuroQoL EQ-5D-3L

The European Quality of Life (Euro-QoL) developed the EQ-5D-3L questionnaire. It is a standardised, self-reported instrument used to evaluate health-related quality of life. It is copyrighted and consists of 5 domains of questions:

1. Mobility
2. Self-care
3. Usual activities
4. Pain/discomfort
5. Anxiety/depression

Each question domain has 3 levels, of which a patient will choose the most appropriate level for each, see [Table 4](#).

Table 4 EQ-5D-3L Scores

Dimension	Response	Score
Mobility	I have no problems in walking about	1
	I have some problems in walking about	2
	I am confined to bed	3
Self-care	I have no problems with self-care	1
	I have some problems washing or dressing myself	2
	I am unable to wash or dress myself	3
Usual activities (e.g. work, study, housework, family or leisure activities)	I have no problems with performing my usual activities	1
	I have some problems with performing my usual activities	2
	I am unable to perform my usual activities	3
Pain/discomfort	I have no pain or discomfort	1
	I have moderate pain or discomfort	2

	I have extreme pain or discomfort	3
Anxiety/depression	I am not anxious or depressed	1
	I am moderately anxious or depressed	2
	I am extremely anxious or depressed	3

The score for each dimension is weighted in accordance with [Table 5](#).

Table 5 EQ-5D-3L Weightings (10)

EQ-5D Dimension	Score = 1	Score = 2	Score = 3
Mobility	0	0.155	0.372
Self-Care	0	0.212	0.326
Usual Activities	0	0.156	0.189
Pain/Discomfort	0	0.112	0.265
Anxiety/Depression	0	0.090	0.204

The following algorithm is then applied to calculate the EQ-5D Total Score:

1. If all five EQ-5D dimensions have a score of 1 then the EQ-5D Total Score is 1.
2. If any of the five EQ-5D dimensions have a score of 3, then the EQ-5D Total Score is:

$$1 - \left(\sum_1^s \text{weighted dimension score} \right) - 0.174$$

3. If none of the five EQ-5D dimensions has a score of 3, then the EQ-5D Total Score is:

$$1 - \left(\sum_1^s \text{weighted dimension score} \right)$$

For the handling of missing weighted dimension scores, see Section [7.6](#).

The Euro QoL EQ-5D-3L Questionnaire is completed at all visits (Inclusion visit, V1, V2, V3, V4, V5, V6 and any additional visits in the case of discontinuation of Tofacitinib).

6.1.1.2.15 SF-12v2 Questionnaire

The short form-12 version 2 (SF-12v2) health survey consists of 12 questions, which evaluate 8 aspects of quality of life (QoL). All items, domain scores and summary measures are scored so that a higher score indicates a better health state. The scores will

be derived based on the guidelines provided in User's Manual for the SF-12v2 Health Survey, Third Edition (4).

Table 6 shows an overview of the SF-12v2 questionnaire domains.

Table 6 Overview of Domains for SF-12v2 questionnaire

Domain	Item numbers
Physical Functioning (PF)	2a, 2b
Role-Physical (RP)	3a, 3b
Bodily Pain (BP)	5
General Health (GH)	1
Vitality (VT)	6b
Social Functioning (SF)	7
Role-Emotional (RE)	4a, 4b
Mental Health (MH)	6a, 6c

SF-12v12 will be considered in terms of the physical and mental component summary measures (PCS_{SF12} and MCS) as well as the 8 health domains seen in [Table 6](#).

The SF-12v2 Questionnaire is completed at all visits (Inclusion visit, V1, V2, V3, V4, V5, V6 and any additional visits in the case of discontinuation of Tofacitinib).

6.1.1.2.16 FACIT-Fatigue Questionnaire

The Functional Assessment of Chronic Illness Therapy-Fatigue (FACIT-Fatigue) questionnaire consists of 13 self evaluated questions. The questions consider the patients functionality over the 7 days prior to completing the questionnaire. Each question has a response of values 0 to 4. The FACIT-Fatigue total score is derived by summing the response to each question which gives a value between 0 and 52. Higher scores represent better patient status (less fatigue).

For some of the questions, the scale indicates a higher score is better and for others a lower score is better. Therefore, in order to correct this and ensure that higher scores represent better patient status, the items marked with a ‘-’ in the

[Table 7](#) will be reversed by subtracting the response from ‘4’ before summing all subscale items.

Table 7 FACIT-Fatigue Item subscale

Item No.	Question	+/-
HI7	I feel fatigued	-
HI12	I feel weak all over	-
An1	I feel listless (“washed out”)	-
An2	I feel tired	-
An3	I have trouble starting things because I am tired	-

An4	I have trouble finishing things because I am tired	-
An5	I have energy	+
An7	I am able to do my usual activities	+
An8	I need to sleep during the day	-
An12	I am too tired to eat	-
An14	I need help doing my usual activities	-
An15	I am frustrated by being too tired to do the things I want to do	-
An16	I have to limit my social activity because I am tired	-

For handling of missing data, see Section 0.

The FACIT-Fatigue Questionnaire is completed at all visits (Inclusion visit, V1, V2, V3, V4, V5, V6 and any additional visits in the case of discontinuation of Tofacitinib).

6.1.1.2.17 PtGA

Patient Global Assessment (PtGA) is measured using a visual analogue scale (VAS) on a 0-100 mm scale, where 0 mm = no symptoms of disease and 100 mm = maximum seriousness which a patient can imagine.

PtGA is measured at all visits (Inclusion visit, V1, V2, V3, V4, V5, V6 and any additional visits in the case of discontinuation of Tofacitinib).

6.1.1.2.18 PhGA

Physician Global Assessment (PhGA) is measured using a VAS on a 0-100 mm scale, where 0 = no disease activity and 100 = maximum disease activity.

PhGA is measured at all visits (Inclusion visit, V1, V2, V3, V4, V5, V6 and any additional visits in the case of discontinuation of Tofacitinib).

6.1.1.2.19 Pain

Pain is measured by the patient using a VAS on a 0-100 mm scale, where 0 = no pain and 100 = maximum pain.

Pain is measured at all visits (Inclusion visit, V1, V2, V3, V4, V5, V6 and any additional visits in the case of discontinuation of Tofacitinib).

6.1.2 Other Endpoints

6.1.2.1 FiRST Questionnaire

Fibromyalgia Rapid Screening Tool (FiRST), used to detect fibromyalgia in patients with diffuse rheumatic pain, is a questionnaire which contains 6 items:

1. Diffuse pain
2. Painful symptoms
3. Fatigue
4. Sleep and cognitive disorders
5. Nonpainful abnormal sensations
6. Functional somatic symptoms

Each of the 6 items contain a yes or no response, and a positive answer to 5 out of the 6 answers can detect fibromyalgia.

The FiRST Questionnaire is completed at all visits (Inclusion visit, V1, V2, V3, V4, V5, V6 and any additional visits in the case of discontinuation of Tofacitinib).

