9.1.6.2. Secondary endpoints

- Change from baseline in catastrophising behaviour adopted by the patient (PCS-Pain Catastrophising Scale)^(34, 35)
- Change from baseline in coping adaptive strategy adopted by the patient (CSQ-Coping Strategies Questionnaire)⁽²⁹⁻³²⁾
- Percentage of patients with low disease activity (LDA) as assessed by DAS28-4 ESR/CRP < 3.2, SDAI ≤ 11, CDAI ≤ 10⁽³⁶⁾,
- Percentage of patients in remission as assessed by DAS28-4 ESR/CRP < 2.6, SDAI ≤ 3.3, CDAI ≤ 2.8, ACR-EULAR 2011 Boolean criteria (TJC ≤ 1 + SJC ≤ 1 + CRP ≤ 1 mg/dL + VAS patient ≤ 1)^(36, 37)
Change from baseline in score DAS28 ESR/CRP and in its components over time
- Evaluation of response to treatment considering outcome of the DAS28 (EULAR criteria)⁽³⁸⁾

Table 1: Evaluation of response to treatment considering outcome of DAS28 (EULAR criteria)

DAS28 at visit	Decrease in DAS28 compared to V0		
	>1.2	>0.6 and ≤1.2	≤0.6
≤3.2	Good responder	Moderate responder	Non-responder
>3.2 and ≤5.1	Moderate responder	Moderate responder	Non-responder
>5.1	Moderate responder	Non-responder	Non-responder

- Change from baseline in the number of painful joints (TJC) over time
- Change from baseline in the number of swollen joints (SJC) over time
- Evaluation of the possible existence of fibromyalgia (FIRST questionnaire)^(39, 40)
- Change from baseline in the duration of morning stiffness over time
- Change from baseline in patient compliance over time (GIRERD Questionnaire)⁽⁴¹⁾
- Change from baseline in overall health status over time (EuroQoL EQ-5D-3L questionnaire)⁽⁴²⁻⁴⁴⁾
- Change from baseline in quality of life over time (SF-12 questionnaire)⁽⁴⁵⁾
- Change from baseline in fatigue over time (FACIT-Fatigue questionnaire)^(46, 47)
- Evaluation of tolerability

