9.3.2. Patient Reported Outcomes

9.3.2.1. PCS questionnaire PCS – *Pain Catastrophizing Scale* (Annexe 3.1):

Catastrophisation of pain affects the manner in which patients perceive pain. In this questionnaire, patients will be asked to describe the type of thoughts and of emotions that they experience when faced with pain ^(34, 35).

The PCS is a 13-item questionnaire (13 thoughts or feelings at time of pain onset) which provides an overall score resulting from the sum of three subscale scores evaluating rumination, exaggeration and helplessness.

The scores for each item are calculated on a 5-point rating scale (0 point for “not at all”, up to 4 points for “all the time”).

PCS total scores range from 0 to 52.

An overall score greater than or equal 20 indicates a clinically relevant level of catastrophisation ^(34, 35, 53).

9.3.2.2. CSQ questionnaire– Coping Strategies Questionnaire (Annex 3.2):

The Coping Strategies Questionnaire (CSQ) evaluates use by the patient of this coping strategy to best deal with and best live with disease/pain ⁽²⁹⁻³²⁾. In its French version, five factors of cognitive coping are evaluated in it: “Distraction”, “Dramatisation”, “Unawareness of painful sensation”, “Reinterpretation” and “Prayer” ⁽³²⁾.

9.3.2.3. GIRERD questionnaire (Annex 3.3):

The GIRERD questionnaire ⁽⁴¹⁾, consisting of 6 questions, is used to evaluate compliance with a medical treatment. The patient is invited to reply “yes” or “no” to each of 6 questions relating to compliance with a prescribed treatment.

- If the patient responds “no” to all questions, he is considered as a good complier.
- If the patient responds “yes” once or twice, he is considered as a minor complier.
- If the patient responds “yes” three times or more, he is considered as a non-complier.

9.3.2.4. FiRST questionnaire -Fibromyalgia Rapid Screening Tool (Annex 3.4):

The FiRST questionnaire (Fibromyalgia Rapid Screening Tool) is a tool for detecting fibromyalgia in patients with diffuse rheumatic pain.

Six items are evaluated: (1) diffuse pain, (2) painful symptoms, (3) fatigue, (4) sleep and cognitive disorders, (5) nonpainful abnormal sensations, (6) functional somatic symptoms. A score of 5 positive items out of 6 items in the questionnaire (Yes/No responses) makes it possible to detect fibromyalgia with a sensitivity of 90.5% and a specificity of 85.7% ⁽³⁹⁻⁴⁰⁾.

9.3.2.5. Euro QoL EQ-5D -3L questionnaire (Annex 3.5):

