8.1.3 Logistic Regression

Logistic regression will be used to analyse the relationship between binary endpoints and behavioural strategies. The binary endpoints will be the response variables at Months 3, 6, 12 and 24 and PSC total score and the 5 domains of the CSQ will be fitted as a continuous, independent variables in separate univariate models. Estimates for the odds ratio's (OR's), confidence intervals (CI's) and p-values will be presented.

Reference code for logistic regression:

```
ODS OUTPUT oddsratios = _out1 parameterestimates = _out2;
PROC LOGISTIC DATA = <data>;
  MODEL <binary endpoint at visit> = <behavioural endpoint at visit>;
  RUN;
  ODS OUTPUT CLOSE;
```

Where ODS OUTPUT option odds ratios selects the OR's and CI's, and parameter estimates can be used to select the p-value.

The association between baseline PCS total score (<20 vs ≥ 20) and baseline characteristics will also be explored using a logistic regression. A univariate analysis will first be performed with a significance level set at 10%. All significant characteristics will be put forward into a multivariate model. A backward selection will be used to remove

characteristics from the multivariate model which do not have a significant p value at the 5% level.

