8.2.6.1 Behavioural Strategies – PCS and CSQ

The impact of behavioural strategies (PCS total score and 5 domains of the CSQ) on Tofacitinib drug survival will be analysed, using three multivariate Cox PH models as described in Section 8.1.1.1 Cox Proportional Hazards.

PCS (individual domain scores and total scores) and CSQ (individual domain scores) will also be summarised as continuous variables as per Section **Error! Reference source not found.** PCS total score will also be summarised as a dichotomous variable (<20 vs ≥ 20) as per Section **Error! Reference source not found.**

Correlations between the behavioural strategies (PCS total score and 5 domains of the CSQ) and each of the endpoints listed below will be investigated as outlined in Section **Error! Reference source not found.**, for the endpoints seen in Figure 3:

- DAS28-4 ESR
- DAS28-4 CRP
- TJC
- SJC
- Duration of morning stiffness
- GIRERD Questionnaire
- EuroQoL EQ-5D-3L
- SF-12v2 Questionnaire
- FACIT-Fatigue Questionnaire
- DAS28 (EULAR Criteria)
- Pain

Figure 3 Timepoints for correlation analyses

Behavioural Strategies Timepoint	Effectiveness Endpoint Timepoint
M0 (Baseline)	M3
M0 (Baseline)	CFB to M3 (M3-M0)
M3	M3
M3	CFB to M3 (M3-M0)
CFB to M3 (M3-M0)	M3
CFB to M3 (M3-M0)	CFB to M3 (M3-M0)
M0 (Baseline)	M6
M0 (Baseline)	CFB to M6 (M6-M0)
M6	M6
M6	CFB to M6 (M6-M0)
CFB to M6 (M6-M0)	M6
CFB to M6 (M6-M0)	CFB to M6 (M6-M0)
M0 (Baseline)	M12
M0 (Baseline)	CFB to M12 (M12-M0)
M12	M12
M12	CFB to M12 (M12-M0)
CFB to M12 (M12-M0)	M12
CFB to M12 (M12-M0)	CFB to M12 (M12-M0)
M0 (Baseline)	M24
M0 (Baseline)	CFB to M24 (M24-M0)
M24	M24
M24	CFB to M24 (M24-M0)
CFB to M24 (M24-M0)	M24
CFB to M24 (M24-M0)	CFB to M24 (M24-M0)

M = Month. CFB = Change from baseline.

Logistic regression will be considered to assess the relationship between behavioural strategies (PCS total score and 5 domains of the CSQ) and each of the binary endpoints listed below as outlined in Section **Error! Reference source not found.**, with a separate model created for each of the timepoints seen in Figure 4:

- LDA
- Patients in remission
- FiRST Questionnaire

Figure 4 Timepoints for logistic regression

Behavioural Strategies Timepoint	Effectiveness Endpoint Timepoint
M0 (Baseline)	M3
M3	M3
CFB to M3 (M3–M0)	M3
M0 (Baseline)	M6
M6	M6
CFB to M6 (M6–M0)	M6
M0 (Baseline)	M12
M12	M12
CFB to M12 (M12–M0)	M12
M0 (Baseline)	M24
M24	M24
CFB to M24 (M24–M0)	M24

M = Month. CFB = Change from baseline.

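### The FiRST logistic models omit FiRST status at inclusion, so an association with baseline behavioural scores may only reflect a positive screen that predates treatment

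*SAP*

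**What the plan says.** SAP 8.1.3 sets the outcome: "The binary endpoints will be the response variables at Months 3, 6, 12 and 24". The PCS total score and the five CSQ domains are "fitted as a continuous, independent variables in separate univariate models", and the reference code has one behavioural term and no baseline term. Odds ratios, confidence intervals and p-values are to be reported.

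SAP 8.2.6.1 gives the purpose: "Logistic regression will be considered to assess the relationship between behavioural strategies" and each listed binary endpoint, namely LDA, remission and FiRST. Figure 4 pairs the behavioural score (at month 0, at the same visit, or as change from baseline) with the endpoint's status at the visit. It has no month 0 to month 0 pair. Change from baseline is allowed for the behavioural score but never for the endpoint, whereas Figure 3, for the correlation analyses, allows it for both.

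FiRST is collected at inclusion and at every visit (SAP 6.1.2.1: "The FiRST Questionnaire is completed at all visits (Inclusion visit, V1, V2, V3, V4, V5, V6"; also Table 1). A patient screens positive on 5 of 6 items, "with a sensitivity of 90.5% and a specificity of 85.7" per cent (Protocol 9.3.2.4). No criterion in Protocol 9.2.1 or 9.2.2 excludes patients who are FiRST positive at entry. FiRST is not among the baseline characteristics related to baseline PCS in SAP 8.2.6.5. SAP 8.1.6 and 8.2.6.4 summarise it per visit, not by inclusion status.

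**The concern.** A patient who screens positive before the first dose and stays positive counts as an outcome positive at months 3 to 24. PCS asks about thoughts during pain, and the FiRST items include diffuse pain and painful symptoms, so some association at inclusion is plausible. If it exists, it carries forward into every model that pairs a baseline score with a later status.

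The analysis serves the objective on behavioural strategies and effectiveness, and the time order in Figure 4 invites a predictive reading. The report could then present as an on-treatment finding an association that was complete before treatment began. None of the behaviour analyses listed in the SAP would show the reader that it was already there at inclusion.

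**Working it through.** **The plan's own figures.** The documents state no figure for the FiRST models, so there is none to reproduce.

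**Number of models.** 6 scores × 12 pairs in Figure 4 = 72 FiRST models: 6 × 4 = 24 with the month 0 score, 24 with the same-visit score and 24 with change from baseline.

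**Inputs not in the documents (assumptions).** FiRST prevalence at inclusion π, persistence r, new positives q, the gap d in baseline score between FiRST-positive and FiRST-negative patients (in SD), and the number evaluable n. SAP 8.2.6 restricts these models to on-treatment assessments, so n is below the planned 300. At the protocol's assumed 50% drug survival it would be about 300 × 0.50 = 150 at month 24.

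**Share of outcome positives already positive at inclusion.** πr / [πr + (1 − π)q]. With r = 0.70 and q = 0.08:
- π = 0.20: 0.140 / (0.140 + 0.064) = 69%
- π = 0.25: 0.175 / (0.175 + 0.060) = 74%

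**Main scenario, month 0 to month 3.** Simulated studies in which later FiRST depends only on inclusion FiRST, so behaviour adds nothing given inclusion status; n = 200 to 250, d = 0.3 to 0.8, π, r and q as above, two-sided 5% test.
- Planned univariate model: odds ratio 1.20 to 1.67 per SD; p<0.05 in roughly 20% to 90% of studies.
- With inclusion FiRST added: odds ratio about 1.00; p<0.05 in about 5%.

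**Wider grid.** π = 10% to 30%, r = 50% or 80%, q = 5%, n = 150 or 250, 1000 studies per scenario:

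| Gap d | Planned month 0 model, p<0.05 | Median odds ratio per SD | Change-from-baseline model, p<0.05 |
|---|---|---|---|
| 0 | 4–6% | 0.98–1.01 | 4–6% |
| 0.3 | 8–40% | 1.15–1.28 | 5–12% |
| 0.5 | 13–77% | 1.28–1.48 | 7–21% |
| 0.8 | 24–99% | 1.42–1.85 | 9–55% |

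Adding inclusion FiRST to the month 0 model brings rejection to 3.5–6.3% in every cell.

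**Why change from baseline is affected less.** The grid takes the follow-up score as 0.6 times the baseline score plus noise. The gap in change is then (0.6 − 1)d = −0.4d. The SD of change is √(0.4² + 1 − 0.6²) = √0.80 = 0.89, so the standardised gap is −0.45d. The distortion is under half as large and reversed in sign: a falling score goes with later positivity.

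**Measurement error.** The return to 5% above follows from letting later FiRST depend only on observed inclusion FiRST. Now use the protocol's accuracy, with stable true fibromyalgia in 10% to 15% of patients, errors independent between visits, and the score gap of 0.3 to 0.8 SD tied to true status. Screen-positive prevalence is 0.10 × 0.905 + 0.90 × 0.143 = 22%, or 0.15 × 0.905 + 0.85 × 0.143 = 26%. The planned model gives p<0.05 in about 10% to 77% of studies, and the adjusted model still does so in about 8% to 41%.

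**The case against.** The plan does not claim that behaviour affects fibromyalgia. The protocol objective is a correlation, the SAP speaks of a relationship, and SAP section 4 states that there are no formal hypotheses. The protocol endpoint is "Evaluation of the possible existence of fibromyalgia (FIRST questionnaire"), not new onset or change. Under that definition prevalent positives are meant to count. In the simulations the baseline score and later FiRST really are associated, so the planned model describes a true marginal relationship. The 20% to 90% is an error rate only if the result is read as something beyond persistence. Every input that drives the size is assumed, and the adjustment works fully only when inclusion FiRST carries no error.

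Most of this stands and limits the point. The 24 same-visit models are legitimate cross-sectional descriptions. What remains is that SAP 8.2.6.1 places FiRST among effectiveness endpoints and pairs a pre-treatment score with on-treatment status, while no planned output separates carry-over from anything arising on treatment.

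A reader might also infer that LDA and remission are free of the problem because patients enter with active disease. The documents do not establish this: eligibility sets no DAS28, SDAI or CDAI threshold. This point makes no claim about those endpoints either way.

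**Conclusion.** The point holds in a conditional form. The omission of inclusion FiRST is plain in SAP 8.1.3 and 8.2.6.1. Its consequence depends on an association between behavioural scores and FiRST at inclusion, which is plausible but not quantified in the documents. With no such association the test keeps its 5% level. With a gap of 0.3 to 0.8 SD under the main assumptions, the month 0 to month 3 model reports an association in roughly 20% to 90% of studies when behaviour adds nothing beyond inclusion status.

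Two stronger readings are tempting. One is that the analysis will show an effect of behaviour on fibromyalgia where none exists. The documents support neither half: no effect is claimed, and whether one exists is unknown. The other is that all 72 models are distorted. The concern is sharpest for the 24 month 0 models, weaker for the 24 change-from-baseline models, and a matter of labelling for the 24 same-visit models. The analysis is secondary and carries no multiplicity adjustment; the primary Cox analysis and the sample size are not touched.

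**What to change.** In SAP 8.1.3 and 8.2.6.1:
- Add FiRST status at inclusion as a covariate in the FiRST models that use the month 0 score or change from baseline. The unadjusted results may be kept alongside.
- Label the 24 same-visit FiRST models as cross-sectional.
- In the SAP 8.2.6.4 summaries, show the FiRST percentage at each visit separately for patients positive and negative at inclusion.

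The cost is one covariate that is already collected and one extra table split. Patients without a FiRST result at inclusion drop out of the adjusted models, so their number should be reported. Because FiRST is measured with error, the report should say that adjustment reduces carry-over but does not remove it.
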